Power. The sample size for the Aim 1 feasibility study is based on our original SHE study pilot and expanded to allow for rigorous testing and refining of modality.²⁶ The sample size of N~200 for the Aim 2 RCT was determined to provide satisfactory power ($\geq 80\%$) for this study in addressing the specific aims, which depends on the following parameters: number of participants (n), number of measurements (t=3 for health literacy for screening; t=4 for screening/risk reduction practices), effect size (f) as group difference in change, correlation between repeated measures (r), and attrition rate. The effect sizes estimated from the original SHE study were in the small to moderate range—for health literacy (8 domains), average $f=0.13$ at immediately post-intervention and 0.16 at 1-year post-intervention; $f=0.17$ for cervix screening and 0.12 for condom use during the last intercourse at 1-year post-intervention. Although effect sizes for breast cancer screening and STI screening are not available from the original SHE study, we expect similar, small to moderate effect sizes for these outcomes. Thus, we conservatively assumed the smallest observed effect size of $f=0.12$ for our power calculation. The correlations between repeated measures observed in the original SHE study were $r=0.46$ on average, with the range of 0.39-0.75 between baseline and immediately post-intervention and 0.25-0.61 between baseline and 1-year post-intervention. Power analysis of these data ($f=0.13$, $t=3$ or 4, $r=0.46$) and G*Power 3.1.9.2 indicated that a sample of 124 women will produce $\geq 80\%$ power for both health literacy (80%) and screening/risk reduction behaviors (85%). In our original SHE study, the 3-year follow-up rate was 85%. Conservatively assuming a high attrition rate up to 40%, we will recruit ~200 women at baseline to adequately power the SHE-Women study—i.e., maintain $\geq 80\%$ power even with a low follow-up rate as small as 60%. As

Table 4. Expected attrition over study period

	Aim 1 feasibility Target N~20	Aim 2 RCT Target N~200	Aim 3 (same as Aim 2)
Consent and baseline	20	260	--
Intervention initiation	15	220	--
Post-intervention	10	200	--
1 year follow-up	--	170	--
2-year follow-up	--	160	--
3-year follow-up	--	150	--

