described above, missing data due to either attrition or nonresponse will be fully recovered via multiple imputation in our intent-to-treat analysis, which will provide additional power and remove any confounding effect of missing data on our statistical power. For Aim 3, the key stakeholder interviews will occur with enough research participants to reach thematic saturation. Based on prior experience with key stakeholder interviews, we believe N~20 interviews will accomplish this goal,²⁷ but have resources to interview additional participants. Additionally, our COVID-19 module interview suggests N~30 interviews will accomplish the goal of thematic saturation.

Outcomes and instruments. Aim 1 feasibility outcomes include uptake of intervention components, barriers and facilitators of implementation, problems with delivery, and necessary modifications.⁴⁵ Pilot effectiveness outcomes will include an assessment of women's health literacy, operationalized as knowledge, beliefs, and self-efficacy for screening related to cervical, breast cancer, birth control, and STIs, post-intervention.^{4,26} Aim 2 RCT outcomes include women's health literacy, immediately post-intervention and 1-year post-intervention; and screening/ risk reduction for cervical, breast cancer, unintended pregnancy, and STIs at 1, 2, and 3-years post-intervention. Aim 3 outcomes include perception and uptake of intervention components.⁴⁵

Feasibility and perception of intervention outcomes are defined below and assessed through participant tracking and key stakeholder interviews with a subset of participants.:

- *Uptake of integrated, multimedia electronic women's health literacy intervention:* documentation of number of participants who responded to text messages; clicks on Website; real-time assessment of knowledge; time elapsed between text messages and Website clicks; number of outreach messages (through text, phone, or Facebook); Facebook posts/messages; chats with health educator; total minutes of contact through text, Web, chat, Facebook with each participant; attendance at community sessions
- *Barriers and facilitators of implementation:* problems described by participants in setting up text message platform, Website, closed Facebook group; factors that make set up of text message platform, Website, closed Facebook group ease of use; ease of Website components use (content modules, assessments)

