Using quantitative data from the pilot trial of the SHE-Women text-Web intervention, we will conduct descriptive analysis and bivariate tests to explore women's health literacy (knowledge, beliefs, and self-efficacy) for screening related to cervical, breast cancer, birth control, and STIs (Aim 1). The results including effect sizes estimated for the outcome will be utilized for refinement of the intervention content and modality. To test the hypothesis that SHE-Women will be more effective than standard of care at improving outcomes (Aim 2), we will utilize mixed modeling techniques for repeated measures, separately for each outcome variable: health literacy for screening and screening/risk reduction practices. General/generalized models will evaluate the effects of the intervention by estimating overall group difference across measurements (i.e., group effect), change over time (i.e., time effect), and group difference in change (i.e., group-by-time interaction). In other words, we will evaluate whether the intervention vs. control group improves in outcomes over time. The models will account for the impacts of sociodemographic characteristics as well as other cross-cutting risk factors including tobacco use, alcohol use, criminal justice involvement, intimate partner violence, lack of continuous health care coverage or primary care contact, etc. (covariates), thereby providing unbiased estimates of the intervention effects. The models for screening/risk reduction behaviors will also consider knowledge about cervix cancer, breast cancer, birth control, or STI as an additional covariate for the respective outcome variable. Incorporating participant tracking data, descriptive analysis and bivariate tests will demonstrate the pattern and uptake of various intervention components as measured by number of participants who responded to text messages; clicks on the Website; interactive clicks on the Website, e.g. through real-time assessment of knowledge; time elapsed between text messages and Website clicks; number of outreach messages (through text, phone, or Facebook); Facebook posts/messages; chats with health educator; total minutes of contact through text, Web, chat, Facebook with each participant; and attendance at community sessions (Aim 3). General/generalized mixed modeling for repeated measures will assess the impacts of the uptake on each outcome variable of health literacy for screening and screening/risk reduction practices while controlling for the impact of sociodemographic characteristics and other risk factors. A proper covariance structure for repeated measures will be chosen for each outcome variable based on model fit (i.e., likelihood, Akaike Information Criterion, adjusted Bayesian Information Criterion). Statistical significance will be determined at 0.05 alpha level, and all analyses conducted using SAS 9.4⁵⁹

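### For the continuous literacy scores, a baseline-adjusted joint test would be more powerful than the implied group-by-time test and needs no new data

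*Combined protocol and SAP*

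**What the plan says.** The Data analysis section fits a separate repeated-measures mixed model to each outcome and assesses SHE-Women through "estimating overall group difference across measurements (i.e., group effect), change over time (i.e., time effect), and group difference in change (i.e., group-by-time interaction". None of the three terms is declared primary. The Power section defines its effect size as "effect size (f) as group difference in change" with three measurements for literacy, so baseline is one of the modelled measurements and the interaction is the implied test.

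On covariates, "The models will account for the impacts of sociodemographic characteristics as well as other cross-cutting risk factors". The list is open-ended and does not name the baseline literacy score. The covariance structure is left to the data: "A proper covariance structure for repeated measures will be chosen for each outcome variable based on model fit".

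For the earlier study, the Power section reports literacy effects of "average $f=0.13$ at immediately post-intervention and 0.16 at 1-year post-intervention". It gives correlations averaging 0.46, "with the range of 0.39-0.75 between baseline and immediately post-intervention and 0.25-0.61 between baseline and 1-year post-intervention". On missing data it says that "missing data due to either attrition or nonresponse will be fully recovered via multiple imputation in our intent-to-treat analysis".

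**The concern.** A group-by-time model with a main effect of group estimates a baseline mean in each arm. In a randomised trial any baseline difference is chance, so estimating it adds noise to every change from baseline. The listed covariates do not remove that noise if they enter as time-constant main effects, because they shift all visits equally and cancel from change.

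The other two terms cannot stand in for the interaction. The group effect averages over baseline, so with three measurements a sustained effect d is diluted to (0+d+d)/3 = 2d/3. The time effect is not a comparison between arms.

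What is at stake is efficiency, not validity. Literacy is one of the two Aim 2 outcome groups. The loss matters most if follow-up falls to the plan's worst case, or if the correlation between baseline and 1 year is near the low end of its range.

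**Working it through.** **Inputs.** From the Power section: f=0.12 (the value it calls conservative), t=3, r=0.46, N=124. From Table 4: 200 women post-intervention and 170 at 1 year. Alpha is 0.05 (Data analysis). Arms are equal in size (Table 3). Compound symmetry is assumed unless stated.

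**Step 1: reproduce the plan's figure.** For the interaction, λ = f²Nt/(1−r) with (t−1) and (N−2)(t−1) degrees of freedom. Then λ = 0.0144×124×3/0.54 = 9.92 and power is 80.7%, matching the stated 80%. At N=170, λ=13.60 and power is 91.8%. At N=120 (60% of 200) it is 79.3%.

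**Step 2: compare precision.** Let I be the identity matrix and J the matrix of ones, both 2×2. Up to a common factor, the covariance of the two follow-up arm differences is

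- free baseline: (1−r)(I + J)
- baseline-adjusted: (1−r)(I + rJ)

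The difference, (1−r)²J, is positive semidefinite, so adjustment never lowers the noncentrality. Only equal and opposite effects at the two visits gain nothing. At a single visit the variance ratio is (1−r²)/[2(1−r)] = (1+r)/2. That is a 27% reduction at r=0.46, 37.5% at r=0.25 and 12.5% at r=0.75.

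**Step 3: noncentrality ratio by effect pattern.** For effects d at the two visits, with s their sum and q their sum of squares, the ratio is [q − rs²/(1+2r)] / [q − s²/3]. At r=0.46, r/(1+2r) = 0.46/1.92 = 0.2396.

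- One visit only (q=1, s²=1): 0.760/0.667 = 1.141
- Halving (2:1; q=5, s²=9): 2.844/2 = 1.422
- Earlier study's pattern (0.13:0.16): 1.545
- Constant (q=2, s²=4): 1.042/0.667 = 1.5625

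**Step 4: power of the joint 2-df test, f=0.12, r=0.46.**

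| Test | λ, N=124 | Power, N=124 | λ, N=170 | Power, N=170 | N for 80% |
|---|---|---|---|---|---|
| Interaction | 9.92 | 80.7% | 13.60 | 91.8% | 122 |
| Adjusted, one visit | 11.31 | 85.8% | 15.51 | 94.9% | 108 |
| Adjusted, halving | 14.10 | 92.7% | 19.34 | 98.1% | 88 |
| Adjusted, 0.13:0.16 | 15.33 | 94.6% | 21.01 | 98.8% | 80 |
| Adjusted, constant | 15.50 | 94.8% | 21.25 | 98.9% | 80 |

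Simulation (6,000 trials per scenario) agrees. At N=124 the interaction gives 80–81% and the adjusted test 85.0%, 92.5%, 94.3% and 94.4%, in the table's order. Type I error over 40,000 null trials at N=124 is 5.1% for both tests.

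**Step 5: sensitivity.**

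- *Attrition as in Table 4* (200 then 170 women): interaction 92.3–96.6%, adjusted 94.9–99.5%.
- *Other r at N=170, f held at 0.12:* 80% to 89–98% (r=0.25); 88% to 93–99% (r=0.39); 98% to 99% or more (r=0.61); no practical gain at r=0.75.
- *f=0.13, r=0.46:* the interaction has 86.9% at N=124 and 95.5% at N=170; the adjusted test has 91.1–97.4% and 97.5–99.6%.
- *Unequal correlations:* these use the plan's ranges with baseline and an assumed 0.3 to 0.6 between the two follow-ups, which the documents do not give. An interaction with 81% power becomes 83–91% (one visit), 87–94% (halving) or 90–97% (constant or 0.13:0.16).

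**Step 6: why not test one visit.** At N=124 an adjusted single-visit test has 89% power for a constant effect. Under 0.13:0.16 it has 80% post-intervention and 93% at 1 year. It has 45% if the effect has halved at the named visit and 5% if it is absent there.

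**The case against.** The strongest reply is that nothing here is wrong. The interaction is a standard, valid test of the question asked, and the open covariate list does not rule out baseline adjustment. That is correct, and the point is put as one of efficiency.

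Second, f=0.12 is the condom-use effect, whereas the literacy effects are 0.13 and 0.16 and the calculation sentence prints 0.13. At 0.13 the gain at N=170 is only 2 to 4 points. This stands as a caveat. But 0.12 is the value the plan says it assumed, and it is the one that reproduces the stated 80% at N=124; 0.13 gives 86.9%. The N=124 figures also need 40% attrition, which Table 4 does not expect.

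Third, two conditions are unverified. Women are surveyed immediately on consent (Intervention arms and procedures) and randomised after consent (control-arm section), but the order of the two is not given. The analysis set is also unclear: Table 4 has 260 at baseline, the Power section about 200, and over-recruitment is meant to replace early losses. Those losses could differ by arm, because only intervention women must initiate a programme. If they are excluded, equal baseline means are no longer assured. Both conditions limit the recommendation.

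Fourth, some covariates, such as tobacco use or health coverage, may vary over time and would not cancel from change. That qualifies the remark about covariates but leaves the baseline difference free. Finally, Table 3 can be read as measuring literacy at 2 and 3 years as well. The study overview, Power and Outcomes sections support two follow-ups, and extra visits would not remove the gain.

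**Conclusion.** The concern holds. For the continuous literacy scores, the implied test uses the baseline data less efficiently than it could. At f=0.12 and r=0.46 the gain is about 5 to 14 points of power at 124 women and about 3 to 7 points at 170. At f=0.13 and 170 women it is 2 to 4 points. It is larger at r=0.25 and negligible at r=0.75. The earlier study's near-constant pattern lies near the top of these ranges, if the ratio of its f values reflects the ratio of the effects.

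The main figures assume compound symmetry, complete data at the stated N and no other covariates. The conclusion also requires a baseline taken before allocation and an analysis set of all randomised women. No gain is claimed for the largely binary screening and risk-reduction outcomes. The change is worth making because it is cheap, not because the planned test is invalid.

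**What to change.** For the literacy scores, before any between-arm outcome analysis:

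1. Fit the same mixed model with baseline means constrained equal across arms (visit terms plus arm-by-follow-up-visit terms, no arm term at baseline). Alternatively, model only the follow-up visits with the baseline score as a covariate.
2. Name the joint test of the arm-by-follow-up-visit terms as the test of the intervention, and report the adjusted difference with its interval at each visit. Do not substitute a single-visit contrast unless that visit is justified in advance.
3. Label the time effect, and the group effect averaged over baseline, as descriptive.
4. State whether every baseline survey was completed before allocation, and that all randomised women are analysed. If either fails, keep the planned interaction.
5. Name arm and baseline score in the imputation model, and pool the joint test across imputed datasets.
6. For binary outcomes, baseline status may be a covariate, but the odds ratio is then conditional and no fixed gain should be claimed.

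The cost is a few sentences in the analysis section and a few lines of SAS, with no new data, visits or participants.

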
Table 1. Justice-involved women's health risk, N=261	N (% or SD)
Cervical cancer risk	
No Pap test in past 3 years	59 (22.6)
Lifetime abnormal Pap test	126 (48.2)
Cervical cancer diagnosis	30 (11.4)
Breast cancer risk	
No mammogram for 50 or older (N=23) in past 2 years	11 (47.8)
Unintended pregnancy risk	
Lifetime unintended pregnancy	207 (79.3)
No past month birth control use (excluding hysterectomy)	76 (29.1)
Sexually transmitted infection risk	
Lifetime STI history	163 (62.4)
No condom use at last sex	196 (75.1)
Ever sold sex	91 (34.8)
Cross-cutting risk factors	
Past month tobacco use	205 (78.5)
Alcohol use problem	132 (50.5)
Past year drug dependence	163 (62.4)
Lifetime mental health diagnosis	191 (73.1)
Past year intimate partner violence	133 (50.9)
Uninsured	160 (61.3)
No primary care doctor	150 (57.4)
No medical home	70 (26.8)
Lifetime months incarcerated, Mean	24.2 (45.3)
Race/ethnic group with higher cancer mortality	
e.g. Black	83 (31.8)
e.g. Hispanic	21 (8.0)
Age, Mean	33.7 (±9.9)

Table 2. SHE-Women - A women's health literacy curriculum

Knowledge of cervical, breast cancer, birth control, and STIs	Beliefs about cervical, breast cancer, birth control, and STIs	Self-Efficacy for cervical, breast cancer, birth control, and STI screening	Confidence navigating health systems for screening and risk reduction
Female body anatomy Medical terminology How stuff works in the body, prevention, and cures Procedures Costs	Beliefs about disease Beliefs about screening Where you learned about sex/health/prevention? What do you share with kids, partners? Romantic/sexual relationship dynamics Experiences with providers Motivations for screening and prevention	What is self-efficacy? Do you know where to go for services/experiences at these places/barriers? Do romantic/sexual partners get in the way/help? How to get results? What makes it easy to get services? Drug use/ homelessness/ transportation/ financial/ other barriers – how to overcome?	Confidence navigating providers given long-term criminal justice involvement? Jail health care and services, trust, cost Outside of jail services, trust, cost, fears Insurance/no insurance Social support for health care seeking Coercion

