Aim 2 RCT settings will be various locations in the Kansas City metro: two urban city/county jails in Kansas City – one facility on the Missouri side of the state line, and one facility in Kansas. We will also recruit women in various community settings with the women having a release date of five years post incarceration. We will recruit women in social support centers, DV shelters, transitional living facilities and other community organizations where our population may frequent. Our goal is to work with women leaving jail or with recent criminal justice involvement using an electronic women's health literacy intervention modality; volunteer for the study; and do not exhibit psychological distress, which would prohibit informed consent. There are no age or medical study exclusions, since all women could potentially benefit for guidance on cervical, breast, unintended pregnancy, and STI screening. For recruitment in jails, we will work with discharge planners to recruit women scheduled to be released from jail. The jail staff will distribute hygiene packets to women as they are being released while introducing the program. Included in these packets, the women will see a business card with our picture and contact info so that if they are interested, they can call us. For sampling, on any given day, about 120 women are incarcerated in the KC, MO facility and 45 women are incarcerated in the KC, KS facility. In local community organizations, we will distribute our 'flyer' that will be placed in the organization, where the population frequents. We will recruit a convenience sample of N~260 women for the RCT, oversampling to account for attrition, with the goal of ending with N~200 women for the RCT. In our previous studies, we have found that in these facilities between 1-4 women are released each day, and that we were

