- *Potential problems with delivery of intervention:* number of incorrect phone numbers, changed phone numbers; problems with Website described by participants and staff; description of level of annoyance with outreach messages through text, phone, and Facebook; number of participants re-incarcerated during intervention trial and, thus, resulted in non-completion; problems with chat feature with health educator
- *Modifications needed to maximize implementation:* suggestions from participants about improving multimedia electronic approaches; suggestions about improving real-time assessments of knowledge
- *Perception of human interaction in intervention:* positive and negative aspects of multimedia electronic educational interventions; benefits and disadvantages to offer of community-based sessions; perceived value of human face in video/audio intervention content; advantages/disadvantages of conversation during discharge planning session for control arm

Women's health literacy and screening/risk reduction outcomes are described in Table 5 below. Items will be adapted from scales listed in Table 5.

Table 5. Women's health literacy and screening/risk reduction outcomes and instruments	
Women's health literacy (Knowledge, beliefs, self-efficacy, confidence navigating systems)	Screening/ Risk reduction
Cervix literacy Pap knowledge scale ⁴⁶ Health belief model scale for cervical cancer and Pap smear test ⁴⁷ Self-efficacy for cancer screening scale ⁴⁸ Confidence navigating health systems scale (cervix, breast, birth control, STI) ⁴	Up-to-date Pap exam or HPV co-testing Abnormal Pap follow-up HINTS cervical cancer screening questions ⁴⁹ Original SHE HPV co-testing and abnormal Pap follow-up questions ⁴
Breast literacy Knowledge, beliefs, self-efficacy items from breast cancer literacy assessment ⁵⁰	Up-to-date screening mammography (biennial) for age 50+ HINTS breast cancer screening questions ⁴⁹
Birth control literacy Contraceptive knowledge assessment ⁵¹ Beliefs about acquisition and use of contraceptive items from self-efficacy scale ⁵²	Current use of hormonal or long-acting reversible birth control method, if no menopause or sterilization BRFSS birth control questions ⁵³
Sexually transmitted infection literacy STD knowledge questionnaire ⁵⁴ Multidimensional condom attitudes scale ⁵⁵ Condom self-efficacy scale ⁵⁶	Condom use at last sex STI treatment BRFSS condom use and STI treatment questions ⁵³

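### The covariate-adjusted mixed model set for every outcome is over-parameterised for mammography, which applies to only about 18 women, and no reduced model is planned

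*Combined protocol and SAP*

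**What the plan says.** The Data analysis section tests Aim 2 with general or generalized mixed models, one for each outcome. Each has a group effect, a time effect and a group-by-time interaction. On covariates it states: "The models will account for the impacts of sociodemographic characteristics as well as other cross-cutting risk factors including tobacco use, alcohol use". It goes on to criminal justice involvement, partner violence and lack of coverage or primary care contact, and leaves the list open. Models for screening and risk-reduction outcomes also take in knowledge in the matching domain. The sociodemographic variables are not named.

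Table 5 defines the breast outcome as "Up-to-date screening mammography (biennial) for age 50" and over. The Power section gives "t=4 for screening/risk reduction practices". The only count of older women is in Table 1 ("Justice-involved women's health risk, N=261"), in the row "No mammogram for 50 or older (N=23) in past 2 years": 11 women, 47.8%.

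The trial has no age quota ("There are no age or medical study exclusions") and recruits 260 women "with the goal of ending with N~200 women for the RCT".

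Only the covariance structure is chosen by model fit. No reduced, penalised or descriptive analysis is given for an outcome that applies to a small part of the sample.

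**The concern.** A model sized for about 200 women is applied unchanged to an outcome that may have fewer than 20. Arm, sociodemographic terms and any risk factor entered at baseline vary between women, not within them, so the number of women limits what can be learned about them. With about as many coefficients as women, a logistic mixed model tends to separate, to give extreme odds ratios, to lose its random-effect variance and to reject a true null hypothesis too often.

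The outcome is not peripheral. Breast screening is one of four screening and risk-reduction areas, and the Validation strategies section counts screening and risk reduction among the primary outcomes. Without a planned alternative, the trial would either report an unstable estimate or drop covariates after seeing the data.

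**Working it through.** **1. The plan's own sample size.** The standard repeated-measures interaction formula is λ = f²·N·t/(1−r), with t−1 and (N−2)(t−1) degrees of freedom. With f = 0.12, N = 124, t = 3 and r = 0.46, λ = 0.0144×124×3/0.54 = 9.92 and power is 80.7%. With t = 4 it is 87.3%. The stated 80% and 85% are therefore roughly reproduced with f = 0.12. The f = 0.13 printed beside the result gives 86.9% and 92.4%. The calculation uses the whole sample for every outcome.

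**2. Women aged 50 and over** (assumption: same share as in Table 1).
- Share: 23/261 = 8.8% (Wilson 95% interval 5.9% to 12.9%).
- Consented: 260×0.088 = 22.9.
- Post-intervention: 200×0.088 = 17.6 (11.9 to 25.8 over the interval), about 9 per arm.
- Years 1, 2 and 3, from the 170, 160 and 150 in Table 4: 15.0, 14.1 and 13.2.
- Not up to date at baseline: 17.6×11/23 = about 8.

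**3. Coefficients.**
- Design, with visit categorical and t = 4: intercept 1 + group 1 + time 3 + interaction 3 = 8.
- Named risk factors: 5 or 6 (coverage and primary care as one term or two).
- Breast knowledge: 1.
- Subtotal: 14 or 15.
- Sociodemographic terms, assumed 3 to 6: total 17 to 21, plus covariance parameters.

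**4. Rows of data.** 18×(1 + 0.85 + 0.80 + 0.75) = about 61 woman-visits, or 18×4 = 72 if every visit is imputed. Imputation fills in visits but adds no women.

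**5. Simulation of the random-intercept logistic model with no treatment effect.** Assumed settings: 12/23 up to date at baseline, random-intercept SD 1.67 or 2.6, and covariate prevalences mostly from Table 1. Share of trials with separation or rank deficiency:

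| Women | 8 coef. | 15 coef. | 18 coef. | 20 coef. |
|---|---|---|---|---|
| 18 | 12–13% | 24–27% | 63–72% | 79–88% |
| 23 | 4% | 7–8% | 37–46% | 40–56% |

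Maximum likelihood fits (SD 1.67, 120 replicates, visits missing at the Table 4 rates):

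| Women, coef. | A coefficient beyond ±10 | Random-effect SD near 0 | Type I error, group-by-time |
|---|---|---|---|
| 18, 8 | 19% | 2% | 11% |
| 18, 15 | 28% | 30% | 23% |
| 18, 18 | 42% | 69% | 15% |
| 18, 20 | 68% | 89% | 23% |
| 23, 18 | 13% | 43% | 9% |
| 23, 20 | 24% | 57% | 9% |

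The Monte Carlo standard error at a true 5% is √(0.05×0.95/120) = 2.0 points. So 15% to 23% is clearly above 5%, while 8% or 9% is only suggestive. With all four visits complete and 18 women, type I error was 8% at 8 and at 15 coefficients, 15% at 18 and 22% at 20.

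**6. Other settings.** Further runs with 18 women were milder:
- With knowledge varying over time, separation or rank deficiency was 10% at 15 coefficients, 46–52% at 19 and 64% at 21.
- It was 11% at 17 coefficients with no rare ethnicity term and with coverage and primary care as one term.
- Another run gave separation in 7–25% over 15 to 19 coefficients, a coefficient beyond ±8 in 16–43%, and type I error of 10–13%.

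Over all runs with 18 women, separation was about 7–27% at 15 coefficients and about 11–88% at 17 to 21.

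**7. Information left without covariates.** The plan's own formula with N = 18 and t = 4 gives λ = 0.0144×18×4/0.54 = 1.92 and power of about 17% (about 20% at f = 0.13).

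**The case against.** A reader might infer that the model cannot be fitted, or that the effect is not estimable. The documents do not support that. There are about 61 to 72 rows, more than the coefficients, and at 15 coefficients most simulated trials showed no separation.

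The coefficient count is also partly constructed. The sociodemographic terms are not listed, and coverage with primary care may be one term. The text does not say that visit is categorical, although the power basis suggests it. Linear time would cut the design terms from 8 to 4; at 13 coefficients in all, separation was 13% with 18 women and 2% with 23.

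The share of older women is projected from a jail-recruited cohort. This trial also recruits through community organisations and friends, so the share could move either way. Women in their late forties at entry could also reach 50 during follow-up.

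A reader might further infer that failed fits would dominate the result pooled over about 200 imputed data sets. No simulation here included imputation, so that is not shown.

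All of this stands as a limit on the stated rates. It does not remove the point. The count of rows overstates the information, because arm and most covariates vary only between women and a two-year screening status asked yearly overlaps from visit to visit. Even with 26 women, the top of the projected range, separation or rank deficiency occurred in 28% of trials at 19 coefficients, against under 1% at 8.

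**Conclusion.** The point holds as one of over-parameterisation. About 14 to 21 coefficients for about 18 women (23 if all consented women count) makes separation, extreme estimates and a type I error above the nominal 5% likely, and the plan has no fallback. How likely depends strongly on the assumed covariates, visit coding and age mix, so no single failure rate should be quoted.

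Removing the covariates cures most of the fitting problem: separation falls to 12–13% in the simulation that gave 63–88% at 18 to 20 coefficients. It does not cure the lack of information. Even the 8-coefficient model showed type I error of 8–11% with 18 women, so an ordinary likelihood-ratio test should not be relied on there either. The point is confined to mammography and does not question the model for outcomes defined on the whole sample. The plan should be changed, but the change is one of wording.

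**What to change.** Add to the Data analysis section, for mammography only:

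- Omit the sociodemographic, risk-factor and knowledge covariates.
- Compare the arms on up-to-date status at one named follow-up visit, with a Firth-penalised or exact logistic model adjusted for baseline screening status. That is three coefficients: intercept, arm and baseline status. The visit must be chosen in advance; if status looks back two years, as in Table 1, only from year 2 does that window lie wholly after the intervention.
- Report the numbers up to date and assessed by arm, with the confidence interval.
- State that the result is descriptive because few women aged 50 and over are expected.
- Say whether age 50 is judged at baseline or at each visit.

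The group-by-time test need not be given up, since it is the plan's stated test. If it is retained for this outcome, fit it without covariates and with a penalised or small-sample method.

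The cost is a few sentences, and no covariate adjustment for this one outcome. The plan justifies the covariates as giving unbiased effects, but randomisation already protects the arm comparison from confounding. No change to recruitment or data collection is needed.
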